## **6.2. Evaluation schedule**

After randomisation patients will visit the hospital every 3 months during the first year and according to local policy thereafter, with at least yearly follow-up visits for at least 10 years.

At each visit, adverse effects will be recorded, physical examination will be performed, and concomitant medication will be registered. Mammography, blood chemistry and haematology will be assessed according to local policy.

## **6.3. Concomitant medication**

Treatment of menopausal symptoms may be initiated as per local policy. Systemic oestrogen therapy is not recommended and when required patients should come off study.

## **6.4. Pathological sub-study**

Detailed histopathological studies on tumour tissue will allow for potential analyses addressing the importance of conventional pathological factors (especially ER and PgR status), as well as a number of newer candidate predictive markers. These investigations will use both conventional multivariate techniques and neural network analysis. See Appendix for more information.

## **6.5. Registration of relapse and death**

In the case of any relapse the adjuvant treatment must be stopped, and this is registered as an event. Full details of relapse should be recorded on the trial Case Report Form (CRF) and returned to the CRCTU. A summary of treatment offered at relapse will also be requested. Any malignant contralateral breast cancer will be registered as a second primary, and relapse with supraclavicular disease will be registered as distant relapse, unless otherwise specifically indicated.

‘Breast cancer’ deaths will be all deaths with breast cancer specified as a cause of death and deaths from any cause following a distant relapse.

All patients will be evaluated for endpoints in the treatment arm to which they were randomised, irrespective of the treatment they actually received. No patient will be removed from the analyses, irrespective of whether she is found to have violated an eligibility criterion after randomisation or to have been withdrawn from trial medication prematurely. Thus analysis will be by “intention-to-treat”, including all patients randomised.

## **6.6. Premature discontinuation**

Patients will be withdrawn from the trial if, in the opinion of the Investigator, it is medically necessary or if it is the wish of the patient. If a patient does not return for a scheduled visit every effort should be made to contact the patient. In any circumstance, every effort should be made to document the patient’s outcome. Particularly, if a patient requests withdrawal from the trial the patient must be asked whether she accepts that her clinical data will continue to be used for trial purposes (in particular, details of disease-related events and follow-up).

Patients will discontinue study treatment in the case of any relapse. Treatment after relapse is at the discretion of the Investigator. Other reasons for a patient to discontinue treatment will be the withdrawal of consent or experience of unacceptable toxicity. There will be no dose modification and the patient will be discontinued from trial treatment should any unacceptable event occur. Information about discontinuation should be recorded in the CRF, and the CRCTU must be informed. **All patients will continue to be followed-up, irrespective of whether they have discontinued treatment prematurely or not.**

## 6.7. Quality of life (QOL) sub-study

A quality of life evaluation has been conducted in patients already enrolled in the study and further enrolment in the QOL study is not required.

## 7. SELECTION OF SUBJECTS

### 7.1. Inclusion criteria

The study population consists of postmenopausal women diagnosed with resectable breast cancer, meeting all of the following eligibility criteria:

- ❑ Histologically/cytologically confirmed early adenocarcinoma of the breast, completely excised by surgery with curative intent (Ro) including:
  - Any node-positive cancer
  - Any cancer  $\geq 3$ cm
  - Node negative cancer, grade II or III and  $\geq 1$ cm
- ❑ ER and/or PgR status positive (as defined by local institutional laboratory)
- ❑ Postmenopausal defined as:
  - Any age:
    - bilateral surgical oophorectomy
    - amenorrhea  $\geq 5$  years (any cause)
    - FSH within institutional postmenopausal range
  - Age  $\geq 50$  y:
    - natural amenorrhea for  $\geq 1$  year, or fulfilling criteria for  $<50$
    - radiation-induced amenorrhea (radiation completed at least 3 months earlier)
  - Age  $< 50$  y:
    - If amenorrhea  $< 5$  years (any cause) or hysterectomy without bilateral surgical oophorectomy, then FSH must be assayed to confirm postmenopausal status
- ❑ Patients on hormone replacement therapy (HRT) which was discontinued at least 4 weeks prior to randomisation are eligible for inclusion
- ❑ Adequate haematological, renal and hepatic function (defined as  $PLT > 100 \times 10^9/L$ ,  $WBC > 3 \times 10^9/L$ , Creatinine  $< 1.5$  UNL and SGOT (AST) or SGPT (ALT)  $< 2.5$  UNL). Normal hepatic function as defined as normal LFTs, or if LFTs were not normal then liver imaging must be normal
- ❑ Accessible for follow-up for the duration of the trial
- ❑ ECOG performance status 0, 1 or 2
- ❑ Written informed consent (according to ICH/GCP and local IRB guidelines)
- ❑ Within 10 weeks of completing surgery +/- adjuvant chemotherapy
- ❑ Patient has had a chest X-ray which showed no evidence of metastases (performed prior to randomisation and no more than 1 month before definitive surgery)

## 7.2. Exclusion criteria

Those patients with:

- Positive supraclavicular nodes
- Evidence of distant metastases (M1)
- Patients whose chemotherapy was started more than 10 weeks after completion of primary surgery
- Patients who have received previous hormonal treatment as adjuvant treatment for breast cancer
- Patients who have received neoadjuvant chemotherapy
- Neoadjuvant hormone therapy > 4 weeks duration prior to surgery
- Severe osteoporosis (bisphosphonates for therapeutic use is not an exclusion criterion)
- Uncontrolled cardiac disease including unstable angina, CHF or arrhythmia requiring medical therapy or with a history of myocardial infarction within the past 3 months or any other serious concomitant disease
- Psychiatric disorders preventing proper informed consent
- Concomitant malignancies except for adequately treated carcinoma *in situ* of the uterine cervix or basal cell carcinoma of the skin. Patients with other malignancies must be disease free for at least 5 years
- Concurrent participation in another clinical study (with the exception of adjuvant cytotoxic chemotherapy trials) involving investigational agents that may interfere with the results of the trial
- Other serious illnesses that may interfere with subject compliance, adequate informed consent or determination of causality of adverse events
- Patients on HRT, which was not discontinued at least 4 weeks prior to randomisation
- Node-negative, grade I cancer < 3cm

## 8. TRIAL ADMINISTRATION & DATA MANAGEMENT

### 8.1. Data management

#### Randomisation

The Investigator must complete a randomisation form prior to randomisation. These details should be phoned or faxed through to the randomisation office at the CRCTU on:

**R A N D O M I S A T I O N O F F I C E**

**☎: [name] or [name]**

**[contact]**

**(9am-5pm, Monday to Friday)**

During the randomisation procedure all eligibility criteria will be confirmed. At the end of the procedure the treatment will be randomly allocated to the patients using a random permuted block method. A sequential Trial Number (TNO) will also be given. This number and the allocated treatment must be recorded on the randomisation form, along with the randomisation date. The randomisation form must be signed by the Investigator and retained in the patient's notes. Confirmation will be sent to the Investigator and the pharmacy of the allocated medication.

### **Case Report Forms (CRFs) - Data Flow**

The CRFs must be completed and signed/dated by the Investigator or one of their authorised staff members as soon as the requested information is available. CRFs will contain common information, but this information will be kept to a minimum. The time between the patient's visit and completion and return of CRF pages should be kept to a reasonable minimum. In all cases it remains the responsibility of the Investigator to check that original CRFs are sent to the CRCTU and to verify that they are completed correctly. The CRFs will be in the form of individual pages, which may be replicated and stored within the Investigator Site File (research folder or patient's notes) and serve as source documents. After completion the original CRF pages must be sent in the prepaid envelope provided to the CRCTU, with copies of the CRFs also stored at site. All sections are to be completed on the CRFs before returning to the CRCTU. If information is not known, this must be clearly indicated by entering NK on the form.

#### **CRFs will include:**

- Randomisation form
- On-study form
- Pathology form
- Follow-up forms
- Adverse Event (AE)/Serious Adverse Event (SAE) forms

To enable monitoring, peer review and/or audits from Health Authorities, the Investigator must agree to keep records, including the identity of all participating subjects (sufficient information to link records e.g. CRFs and hospital records), all original signed Informed Consent Forms, copies of all CRFs and detailed records of drug disposition. To comply with international regulations these records should be retained by the Investigator for 15 years, including assessments such as CT scans.

## **9. MONITORING**

**TEAM** is being conducted under the auspices of the Cancer Research UK Clinical Trials Unit, at The University of Birmingham according to the current guidelines for Good Clinical Practice. Participating centres will be monitored by CRCTU staff to confirm compliance with the protocol and the protection of patients' rights as detailed in the Declaration of Helsinki (Appendix 4).

All clinical Investigators taking part in the trial will be asked to sign a commitment statement and supply a current CV to the CRCTU. All clinic personnel should attend a start-up meeting/initiation visit for training on study procedures and data collection methods. The lead Investigator must submit this protocol, any supporting documentation, and any subsequent amendments to a Local Research Ethics Committee (LREC) and, if locally required, Institutional Review Boards. Investigators must acquire LREC approval and forward a copy of the written LREC approval letter, signed by the Chairman, to the CRCTU before they commence recruitment.

All participating centres will be visited by the CRCTU monitoring team shortly after they begin recruiting, and at the mid- and end-points of the study. The **TEAM** Trial Coordinator will be in regular contact with centre personnel (by phone/fax/email/letter) to check on progress and any

queries that they may have. Study staff will check incoming forms for compliance with the protocol, consistent data, missing data and timing. Investigators will allow the monitors access to source documents as requested. If required the monitoring team will visit centres on a more frequent basis. Centres may be barred from further recruitment in the event of serious and persistent non-compliance and/or very poor recruitment.

A pre-study and/or site initiation visit to determine the qualifications of the Investigator(s), to inspect the clinical laboratory facilities, and to fully inform the Investigator of their responsibilities and the procedures for assuring adequate and correct documentation may be conducted on behalf of the UK **TEAM** Steering Committee, if deemed necessary.

Monitoring of the individual centres will take place on a regular pre-determined basis, but monitoring will be confined to a minimum.

Data to be verified will include Informed Consent, eligibility, adverse events and outcome. Any major problems identified during monitoring will be reported to the UK **TEAM** Steering Committee.

All records will be maintained in accordance with local regulations and in a manner that ensures security and confidentiality.

The completed original CRFs are the sole property of the UK **TEAM** Steering Committee and should not be made available in any form to third parties (except for authorised representatives of appropriate Health/Regulatory Authorities) without written permission from the UK **TEAM** Steering Committee.

## **10. ASSESSMENTS AND FOLLOW-UP SCHEDULE**

### **10.1. Pre-randomisation**

*To be recorded in the patient notes if not included on the CRFs*

- Relevant medical history
- Serious acute or chronic conditions
- Cardiac history
- Thromboembolic history
- Rheumatological history
- Demography (date of birth)
- Concomitant medication (description of other medication prescribed for more than 7 days and taken within one month of randomisation)
- Clinical examination including height and body weight
- ECOG performance status

### **10.2. On-study**

*To be recorded in the patient notes if not included on the CRFs*

- Relevant medical history (relevant surgical resections, conditions that need medical intervention e.g. cardiac ischaemia or arrhythmia, COPD, gastric ulcer etc.)
- Clinical examination including vital signs and body weight (Appendix 1)
- WBC with differential and platelet count and blood chemistry (creatinine, bilirubin, AST and/or ALT, calcium, alkaline phosphatase and glucose)

- ❑ Concomitant medication (other medication prescribed for more than 7 days) and adverse events
- ❑ Mammography (performed according to local policy)
- ❑ Other tests at the discretion of the Investigator
- ❑ During the first year only (at baseline and months 3 and 12) the QOL questionnaire will be completed (applicable to previously randomised patients only)

### 10.3. Follow-up evaluation schedule

After randomisation, patients will visit the centre every 3 months for the first year and have long-term follow-up of at least 10 years irrespective of whether they have withdrawn from treatment prematurely. Follow-up data should include sites of recurrence, time of recurrence, subsequent treatment, mortality, and cause of death. Information on second primary breast cancers and other second primary tumours will also be recorded.

During follow-up visits at 1 to 5 years, physical examination will be performed, concomitant medication will be registered and adverse events (if any) will be recorded. Mammography, blood chemistry and haematology will be assessed according to local policy. During follow-up visits at 6 to 10 years patients will be seen according to local policy.

**Figure 1: Trial Data Flowchart**

Year						Follow-up (year 1 to 5)	Follow-up (year 6 to 10)
	1	2	3	4	5	6-10	11-15
Visit							
Within months	0	3	6	9	12	12-60	60 - 120
Medical history	X						
Initial data 	X						
Clinical examination	X	X	X	X	X	X	Follow-up should be carried out annually according to local policy
Events (if present)		X	X	X	X	X	
Co-medication 	X	X	X	X	X	X	
Adverse Events/SAEs 	X	X	X	X	X	X 	
Mammography	X					Local policy	
Quality of Life (QOL)	X	X			X		

Notes:

1. Type of primary surgery, tumour pathology and characteristics, pre-existing medical conditions.
2. Any medication **prescribed** and used for more than 7 consecutive days.
3. As described in section 12, 'Adverse Events'.
4. After completion of study treatment, adverse events need only be recorded if they occur within 30 days of the last dose of study medication (section 12).

#### **10.4. Follow-up**

All patients should have long-term follow-up, irrespective of whether they have been withdrawn from treatment prematurely. The anticipated follow-up frequency is once every year, unless otherwise clinically indicated. Follow-up after relapse should be according to local policy.

Should a patient be discharged to GP care or another hospital, a Transfer of Follow-up Form must be completed. Thereafter, follow up information must be collected from these sources on an annual basis and sent to the Trials Office. Should the GP or other hospital be unable to provide this information the Trials Office should be informed.

#### **To be recorded:**

- Trial events (end-points)
- Survival
- Important information relevant for the trial (unforeseen circumstance that may have led to changes in interpretation of the results, for instance, cause of death)

**Note: Disease relapse** is defined as the appearance of locoregional recurrence (in a patient with a mastectomy) or distant metastases at any site. Ipsilateral recurrence in a patient treated by lumpectomy or contralateral new breast cancers are not considered as relapses. Time to first locoregional recurrence or distant recurrence will be recorded on separate parts of the CRF. In the event of relapse (locoregional for mastectomy or any distant site), adjuvant hormonal treatment must be stopped. For patients with a lumpectomy and ipsilateral recurrence without distant relapse and for patients with new contralateral breast cancers, adjuvant hormonal treatment may continue at the discretion of the Investigator. All patients must be followed-up, irrespective of whether their recurrence is distant, local or consists of a second (breast) primary. Date of suspicion of relapse, action taken to confirm relapse and date of relapse confirmation will all be recorded on the CRF.

#### **Events that should be recorded are:**

- Locoregional recurrence
- Contralateral recurrence (new primary)
- Supraclavicular nodal relapse
- Distant relapse
- Death and cause of death (breast cancer/other)
- Other second malignancies
- (Serious) Adverse Events

#### **10.5. Procedure for introducing protocol change**

Patients currently enrolled in the *TEAM* trial should be informed of the change in trial design and the reasons for this. All patients currently on allocated study therapy should be provided with the Patient Information Sheet (for current participants). Different Patient Information Sheets are available for patients allocated tamoxifen and those allocated exemestane. All patients should be requested to complete and sign a new Consent Form.

Patients currently taking exemestane will continue their planned therapy without alteration. Patients currently taking tamoxifen should be supplied with exemestane no earlier than 30 months from randomisation and no later than 36 months. Patients who will reach the switch window limit before the next scheduled visit should be recalled early. All other patients should be informed at their next follow-up visit. There is no requirement for additional visits or postal contact, however individual Investigators may wish to contact patients and invite them to discuss the change early.

## **10.6. End of Study**

For the purposes of Clinical Trial Authorisation (CTA) under the European Union Directive 2001/20/EC, the study is deemed to have ended 30 days after the last patient receives the last dose of the Investigational Medicinal Product (IMP).

For the purposes of Multicentre Research Ethics Committee approval, the study end date is deemed to be the 6 months after the date of last data capture.

## **11. WITHDRAWAL**

Patients have the right to withdraw from the study at any time for any reason. The Investigator also has the right to withdraw patients from the study. Full details of the reasons for withdrawal should be recorded on the CRF if clinician initiated, otherwise a simple statement reflecting patient preference will suffice. Withdrawn patients should continue to be followed-up in accordance with the protocol with their permission.

A patient will be withdrawn from the trial if any of the following occur:

- Relapse (appearance of metastatic cancer)
- The patient, in the opinion of the treating physician, is unable to tolerate the toxicity resulting from the hormonal treatment
- Non-adherence with protocol/treatment
- Refusal and/or reservations of the patient to continue treatment or withdrawal of consent.
- Patient lost to follow-up

The date and reason for discontinuation must be recorded on the CRF. Every effort should be made to complete the appropriate assessments.

## **12. ADVERSE EVENTS: DEFINITIONS AND REPORTING**

### **12.1. Procedures for collecting Adverse Events**

All medical occurrences (which meet any of the following definitions) from the first dose of Investigational Medicinal Product (IMP) to 30 days after the last dose of IMP should be reported as adverse events and must be accurately recorded on the appropriate trial CRF and sent to the **TEAM** study office.

In addition, any known untoward event that occurs subsequent to the adverse event-reporting period that the Investigator assesses as possibly related to the IMP should also be considered an adverse event and reported accordingly.

Toxicities will be reviewed using the National Cancer Institute Common Toxicity Criteria (NCI CTC version 2.0). Appendix 5 shows a selection of the NCI CTC; a full list can be found in your Investigator Site File or you can request a copy from the CRCTU. Any toxicities incurred but not categorised by the NCI CTC should be graded by the physician and be recorded on the CRF using a scale of (1) mild, (2) moderate or (3) severe (as defined in Appendix 6). For each sign/symptoms, the highest grade observed since the last visit should be recorded.

**Please note the following:**

- ❑ **A pre-existing condition should not be reported as an adverse event unless the condition worsens or episodes increase in frequency during the adverse event-reporting period**
- ❑ **Symptoms of the targeted cancer or relapse with breast cancer (relapse being a study endpoint) should not be reported as adverse events**

## **12.2. Adverse event definitions**

### **Adverse Event (AE)**

An Adverse Event (AE) is defined as any unfavourable and unintended sign, symptom or disease in a clinical trial subject temporarily associated with the use of an Investigational Medicinal Product (IMP); the event need not have a causal relationship to the IMP.

### **Adverse Reaction (AR)**

An Adverse Reaction (AR) is defined as all untoward and unintended responses to an IMP related to any dose administered. An AR is therefore an adverse event where a possible causal relationship between the IMP and the adverse event cannot be ruled out.

### **Unexpected Adverse Reaction (UAR)**

An Unexpected Adverse Reaction (UAR) is defined as an AR that in nature or severity is not consistent with the applicable product information (e.g. is not listed as a known toxicity in the protocol, the Consent Form, the package insert, the Investigator File, Investigator Brochure or Summary of Product Characteristics).

### **Serious Adverse Event (SAE)/Serious Adverse Reaction (SAR)**

An Serious Adverse Event (SAE) or Serious Adverse Reaction (SAR) is defined as any medical occurrence that at any dose is fatal or life-threatening (i.e. results in an immediate risk of death); is permanently or substantially disabling; requires or prolongs hospitalisation (only if related to an unexpected complication); or is a congenital anomaly, a new primary cancer (excluding breast cancer) or medication overdose. This category also includes any other event the Investigator judges to be serious or which would suggest a significant hazard, contra-indication, side effect or precaution.

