### Exemestane safety in early breast cancer

The IES study has provided information on the safety and tolerability of exemestane given for 2-3 years after prior tamoxifen therapy (Table 3). In general this is reassuring in comparison to continued tamoxifen, however there is an increase in the incidence of osteoporosis compared to tamoxifen.

**Table 3:** Adverse events in the IES study significantly different, or different by >1%, or common (>5%)

Adverse events any grade	Exemestane % (n = 2309)	Tamoxifen % (n = 2332)	p value
Arthralgia	5.4	3.6	0.01
Diarrhoea	4.3	2.3	0.001
Thromboembolic AEs	1.0	2.0	0.01
Thromboembolic SAEs	1.3	2.4	0.005
Vaginal bleeding	4.0	5.6	0.01
Other gynaecological symptoms	5.8	9.0	<0.001
Endometrial cancer	0.21 (5 events)	0.46 (11 events)	Not stated
Other malignancy	22	42	Not stated
Cramp	2.8	4.4	0.0007
Sweating	18.6	18.1	
Headache	18.6	16.4	0.09
Dizziness	12.5	12.1	0.93
Visual disturbance	7.4	5.8	0.04
Depression	5.2	4.0	
Osteoporosis	7.4	5.7	0.05
Clinical fracture	3.1	2.3	0.08

Bone toxicity is clearly an important factor in the use of aromatase inhibitors in early breast cancer. Exemestane has been compared to placebo in a randomised study of postmenopausal women with invasive or pre-invasive breast cancer where the risk of recurrence was considered too small to warrant routine adjuvant treatment. In this study exemestane was associated with a

modest and non-significant difference in Bone Mineral Density (BMD) loss in the lumbar spine over 1 year, 2.2% vs. 1.8%, and a small but statistically different BMD loss at the hip, 2.7% vs. 1.5% (p= 0.02). Bone studies from IES are expected to report shortly. Currently no specific recommendations for the management of bone health in women taking aromatase inhibitors is available, however there is evidence that bone loss in premenopausal women treated with ovarian suppression and zoledronic acid can prevent BMD loss. Women diagnosed with osteoporosis whilst taking aromatase inhibitors would be candidates for bisphosphonate therapy. The field of bone health in women taking adjuvant aromatase inhibitors is the subject of active research: with some patients currently enrolled in the *TEAM* study participating in a bone biomarker substudy and BMD studies ongoing in the Netherlands and Germany.

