### **Suspected Unexpected Serious Adverse Reaction (SUSAR)**

A Suspected Unexpected Serious Adverse Reaction (SUSAR) is defined as a SAR that has not been previously documented in the product literature, the nature and severity not being consistent with the product information.

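### The UK/ROI protocol lets hospitalisation count as serious only for an undefined unexpected complication, so whether an admission for a known toxicity is an SAE rests on discretion

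*Protocol*

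**What the plan says.** Three definitions in Protocol section 12.2 bear on this point.

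- **SAE/SAR.** The definition begins with "any medical occurrence that at any dose is fatal or life-threatening (i.e. results in an immediate risk of death" and goes on to lasting or major disability. It then adds an event that "requires or prolongs hospitalisation (only if related to an unexpected complication", and after that congenital anomaly and "a new primary cancer (excluding breast cancer) or medication overdose". A closing sentence adds "any other event the Investigator judges to be serious or which would suggest a significant hazard, contra-indication, side effect or precaution".
- **UAR.** A reaction is unexpected when its nature or severity does not fit the product information, for example when it "is not listed as a known toxicity in the protocol, the Consent Form, the package insert" or the other reference documents named there.
- **SUSAR.** This is "a SAR that has not been previously documented in the product literature".

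Table 3 in section 3.4 gives the toxicities seen in the earlier switching trial of exemestane after tamoxifen. They include clinical fracture (3.1% exemestane, 2.3% tamoxifen) and a separate line for "Thromboembolic SAEs" (1.3% and 2.4%).

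**The concern.** Seriousness describes how bad an event was. Expectedness describes whether it was already known. Sections on the UAR and SUSAR keep the two apart, but the hospitalisation criterion joins them. An admission for a toxicity the protocol already lists may then not count as serious on that ground, and listed toxicities are the ones on which the two regimens are expected to differ.

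SAE status has consequences in this protocol:

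- Section 12.3 requires a form within 24 hours, onward notification to the company, regulators and ethics committees, and inclusion in the annual report.
- Section 12.4 gives SAEs a longer follow-up rule than other adverse events, without the cut-off at the start of other anti-cancer treatment.
- Appendix 6 requires a relatedness determination for every SAE.
- Section 16 has the DSMC monitor SAEs.

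The relative safety of the arms is a secondary objective (section 5). If similar admissions are classified differently from site to site, the committee sees an uneven SAE record. Because treatment is open label, the allocated drug is known to the person exercising the judgement.

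**Working it through.** No figure is stated on this point, so there is nothing to reproduce. The check sets the definitions side by side.

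1. **Is the condition confined to one criterion?** Yes. Death, threat to life, disability, congenital anomaly, new non-breast cancer and overdose all stand without any test of expectedness. Only hospitalisation carries one.

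2. **What does the condition mean?** The protocol does not define an unexpected complication. The nearest definition is that of the UAR: an event whose nature or severity does not match the listed information, including "is not listed as a known toxicity in the protocol".

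3. **Apply that meaning to a worked case.** Take a deep vein thrombosis needing anticoagulation (grade 3 in Appendix 5) that leads to admission, poses no immediate risk to life and leaves no lasting disability.
   - Thromboembolic events are listed in Table 3, so the complication is expected in nature.
   - Unless its severity is out of line with the product information, the hospitalisation criterion fails.
   - No other automatic criterion applies.
   - The event becomes an SAE only through the closing sentence.

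   A fracture that is admitted and heals without major disability follows the same path.

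4. **Compare with the SUSAR step.** A SUSAR is picked out from among SARs by asking whether the reaction was already documented. That step presumes that documented, and therefore expected, SARs exist. On the reading in step 2, a reaction that is serious through hospitalisation alone has already passed an expectedness test before it reaches the SUSAR step. The second test then has almost nothing left to separate. The definitions do not fit together.

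5. **Which events are captured in any case?** Endometrial cancer is always an SAE, as a new non-breast primary cancer. Fatal, life-threatening and disabling events are SAEs whether expected or not.

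6. **Does the planned safety comparison change?** No. Section 15.5 tabulates all adverse events by arm and by worst CTC grade, with a Chi-square test where judged clinically important. Sections 12.1 and 12.4 require all adverse events on the CRF up to 30 days after the last dose, subject to the section 12.4 cut-off at other anti-cancer treatment. SAE status plays no part in that table.

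7. **How many patients fall under this wording?** Section 15.1 says each country has its own protocol, and the others are not shown. Section 15.2 gives about 1200 UK patients out of 9300: 1200 / 9300 = 12.9%.

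8. **How many events?** This cannot be derived. The protocol gives no rate of hospitalisation for any listed toxicity.

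**The case against.** The strongest reply is that the conflict is imported. The UAR definition concerns adverse reactions judged against product information. The SAE definition speaks of a complication and covers any medical occurrence, related or not. The parenthesis may have been meant only to keep planned admissions out. This is a plausible intention, but the text does not state it, and two sites could reasonably classify the same admission differently. The UAR definition also turns on severity as well as nature, so an unusually severe case of a listed toxicity could still count as unexpected. That narrows the gap without closing it.

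A second reply is that the closing sentence covers any event suggesting a significant hazard or side effect, as an alternative to the investigator's own view of seriousness. This is right, and it means such admissions can still be reported as SAEs. It nevertheless leaves the decision to judgement where the other criteria are automatic.

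Two stronger readings are tempting, and the protocol does not support either.

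- **That admissions for known toxicities fall outside SAE reporting altogether.** They fail one criterion and may enter by others.
- **That the clause costs the trial power, or inflates error, in comparing serious toxicities.** A reader might apply the Table 3 rates to 4650 patients per arm and discount them for lost events. The share lost would be an assumption, section 15.5 plans no test of SAE rates, and the calculation would extend UK/ROI wording to every country.

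**Conclusion.** The point holds as a defect of definition. In the UK/ROI protocol, seriousness by hospitalisation depends on an undefined term that overlaps with expectedness. For admissions that are not fatal, life-threatening, disabling or due to a new non-breast cancer, SAE status for a listed toxicity can turn on discretion. The effect is on consistency of SAE classification, 24-hour reporting, SAE follow-up and the DSMC's review of SAEs.

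The size in events is unknown, and no power or type I error figure follows from the protocol. The conclusion rests on reading the undefined term in the light of the UAR definition. If the term was meant to exclude only planned admissions, the remedy is still to say so. The main toxicity comparison stands as planned. The wording should be corrected, but it does not threaten the trial's validity.

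**What to change.** Reconcile the SAE, UAR and SUSAR definitions in section 12.2.

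- Replace the parenthesis with an exclusion of planned or elective admissions only. For example: *an inpatient admission or the extension of one, except where the admission was planned or elective*.
- State that the section 12.1 note still applies, so that relapse and symptoms of the cancer under treatment are not reported as adverse events. Without this, a wider hospitalisation criterion would read against that note.
- Leave expectedness to the UAR and SUSAR definitions alone.
- Check whether the other country protocols carry the same parenthesis, so that SAEs pooled for the DSMC are defined alike.

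The cost is a one-sentence amendment and more SAE forms for known toxicities.
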